6.4.2.2 Time to Progression according to RECIST v1.1 criteria by investigator determination

This secondary endpoint is time to progression. TTP is defined as the time from date of randomization until date of radiological progression according to RECIST v1.1 criteria by investigator determination.

6.4.2.3 Quality of Life Assessments (FACT-Hep)

6.4.2.3.1 FACT-Hep Scores

The total score of the FACT-Hep QoL instrument will be calculated, the scores of each domain (Physical Well-Being, Social/Family Well-Being, Emotional Well-Being, Functional Well-Being), Hepatobiliary Cancer subscale (HCS), FACT-hep trial outcome index and each question at each time-point and their differences from baseline will be determined for each treatment group.

The scoring algorithm is in Section 11.3 Appendix 3.

6.4.2.3.2 Time to Deterioration in QoL (TTDQoL)

The time to deterioration in QoL is defined as the time from date of randomization to the assessment date when the change from baseline in FACT-Hep Total Score is ≤ -7 points (i.e., a 7 point or greater decline in the total score) or date of death, whichever occurs first.

6.4.2.4 Time to Untreatable Progression

This secondary endpoint, time to untreatable progression, is defined as the time from date of randomization to date of untreatable progression, where untreatable progression is defined as one of the following events:

- Intolerance to sorafenib
- Occurrence of specific contraindications to sorafenib
- Assessment of progression in the target lesions, occurrence of new lesions after treatment, or death due to progression and, for patients randomized to the treatment group, a maximum of 2 re-treatments with TheraSphere
- Occurrence of specific contraindications to TheraSphere and or appearance of lung/intestinal shunts or anatomical constraints not correctable by radiological procedures for the Treatment group
- Confirmed extra-hepatic metastases
- Deterioration of liver function (Child Pugh score $>B7$)
- Clinical progression to ECOG performance status >1 . Such deterioration in performance status should be observed at two subsequent evaluations at 8 week intervals.

The investigator will determine whether the patient met any of the protocol specified conditions. A response of yes to the question of “Is this progression considered untreatable according to the protocol definition?” on the Determination of Response or Progression CRF page will be used to indicate untreatable progression.

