8.6.2.2 Time to Untreatable Progression (TTUP)

TTUP rates will be derived from the Kaplan-Meier estimates for each treatment group; 3, 6, 9, and 12 month TTUP rates will be presented, together with 95% CIs. Quartiles will

be presented and 95% CIs interval will be calculated on the quartiles for each treatment group. A log-rank (two-sided) test will be used to compare TTUP between the two treatment groups at a 0.05 significance level. The HR and corresponding 95% CI will be computed from a Cox proportional hazards model. Plots of the Kaplan-Meier curves will be provided for each treatment group. This analysis will be performed on both the mITT and PP populations.

TTUP (Months) = (Date of event/censor – Date of Randomization +1)/ 30.4375.

The censoring is performed in the following order:

- 1) If a patient does not have a baseline tumor assessment, then the TTUP time will be censored at the randomization date, regardless of whether or not untreatable PD has been observed.
- 2) If a patient received a subsequent HCC therapy before untreatable PD or in the absence of untreatable PD, the TTUP time will be censored at the last valid (i.e. evaluable) post baseline radiological tumor assessment on or before the start date of the subsequent HCC therapy. If the patient has no valid post-baseline radiological tumor assessments on or before the start date of the subsequent HCC therapy, the patient will be censored at the randomization date.
- 3) If a patient is known not to have untreatable PD and did not receive subsequent HCC therapy, the TTUP time will be censored at the date of death or last valid post baseline radiological tumor assessment date in the absence of death, or at the randomization date if the patient does not have any valid post-baseline radiological tumor assessments or death.
- 4) If a patient had untreatable PD immediately after two or more missed visits (Note: a response of NE for a visit is not considered as a missed visit), the patient will be censored at the time of the last valid post baseline radiological tumor assessment date that occurred before the missed visits. If the patient has no valid post-baseline radiological tumor assessments before the missed visits, the patient will be censored at the randomization date.

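### SAP 6.4.2.4 defines TTUP by seven kinds of event but names one progression-page question as its only event indicator, so non-imaging events and progression deaths can be missed and then censored

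*SAP*

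**What the plan says.** SAP 6.4.2.4 measures TTUP from randomization to untreatable progression, "where untreatable progression is defined as one of the following events", and lists seven items. The first is simply "Intolerance to sorafenib". Others are contraindications, Child-Pugh above B7, and ECOG above 1, of which it says "Such deterioration in performance status should be observed at two subsequent evaluations at 8 week intervals". The third item reads in part "Assessment of progression in the target lesions, occurrence of new lesions after treatment, or death due to progression".

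The same section then has the investigator judge the listed conditions. It takes as the event indicator a yes to a single question, asking whether the progression is untreatable under the protocol's definition, "on the Determination of Response or Progression CRF page will be used to indicate untreatable progression".

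SAP 8.6.2.2 sets the censoring. Rule 2 censors at the last valid scan when subsequent HCC therapy starts without a prior untreatable PD. Under rule 3, for patients with neither untreatable PD nor subsequent therapy, "the TTUP time will be censored at the date of death or last valid post baseline radiological tumor assessment date". A sensitivity analysis then removes censoring at death, but only for deaths from causes other than progression.

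The protocol describes the endpoint in two ways. Section 10.2.2.2 speaks of time to radiological progression and then lists what makes it untreatable. Section 10.2.3.2 counts the first of the listed events, and the synopsis likewise accepts RECIST progression, contraindication or performance status.

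**The concern.** The variable to be programmed may not be the endpoint that is defined. The indicator is worded about a progression and sits on a response/progression page. A patient who becomes untreatable with no progression recorded has no stated route into the event count and no stated event date. If the answer is not yes, the censoring rules treat that patient as still treatable up to the last scan or death.

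Such censoring could be informative and need not balance between arms. Controls start sorafenib as soon as possible after randomization. TheraSphere patients generally start 2 to 6 weeks after all initial lesions are treated, and a second lobe is treated in weeks 5 to 8. Early exposure to the sorafenib-intolerance item therefore differs by arm. The trial is open-label, so a single investigator answer deciding the event carries more weight than it would under blinding.

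TTUP is a secondary endpoint tested at two-sided 0.05 within the hierarchy of SAP 8.6.2, so its definition bears on a confirmatory claim.

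**Working it through.** The documents give no TTUP event count, effect size or power, so there is no figure to reproduce. The check is a comparison of texts, followed by an illustration on assumed inputs.

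**Step 1. Each item against its stated route.** Dates held elsewhere are taken from the OS censoring text and list in SAP 8.6.1.

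| Item in SAP 6.4.2.4 | Needs an efficacy scan? | Dated elsewhere in the eCRF? |
|---|---|---|
| Sorafenib intolerance | No | Sorafenib stop dates; intolerance itself not defined |
| Sorafenib contraindication | No | No field shown |
| Target-lesion progression or new lesions | Yes | Imaging date |
| Death due to progression (same bullet) | No | Confirmation of Death page; no cause item shown |
| TheraSphere contraindication, shunt or anatomy | No | No field shown |
| Extra-hepatic metastases | Yes | Imaging date |
| Child-Pugh above B7 | No | Child-Pugh assessment date |
| ECOG above 1, confirmed | No | ECOG assessment date |

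The only route named for any row is the one CRF question. SAP 8.6.1 associates the Determination of Response page (its name differs slightly there) with an imaging date. None of the other dates is used for TTUP. For TTSP, by contrast, SAP 6.4.2.5 already derives confirmed ECOG above 1 by algorithm and dates it to the first such assessment.

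**Step 2. Three patients without a recorded yes.**

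- *Stops sorafenib for intolerance, then starts another systemic therapy.* By the definition this is an event at intolerance. Under rule 2 the patient is censored at the last scan on or before the new therapy.
- *Child-Pugh rises above B7 with no radiological PD and no further therapy.* By the definition this is an event at that assessment. If the patient is handled as free of untreatable PD, rule 3 censors at death or the last scan.
- *Dies of progression with no earlier event.* SAP 6.4.2.4 makes this an event. Rule 3 can be read as censoring at death. The sensitivity analysis implies that only other deaths are censored. Two programmers could code this patient differently.

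**Step 3. Can the direction of bias be settled?** Assume constant hazards. Let a share q of control-arm events be non-radiological, take the radiological hazard ratio as 0.754 (borrowed from the OS design, only to have a number), and let h be the non-radiological hazard ratio. If every non-radiological event is missed and censored, the derived HR is 0.754. The HR as defined is

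(1 − q) × 0.754 + q × h.

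| q | h = 0.6 | h = 1.0 | h = 1.25 |
|---|---|---|---|
| 0.1 | 0.739 | 0.779 | 0.804 |
| 0.3 | 0.708 | 0.828 | 0.903 |
| 0.5 | 0.677 | 0.877 | 1.002 |

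For example, with q = 0.3 and h = 1.0: 0.7 × 0.754 + 0.3 × 1.0 = 0.5278 + 0.3 = 0.828. The derived 0.754 lies above the defined value in the first column and below it in the other two, so the bias can go either way. Neither q nor h is in the documents.

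**The case against.** The strongest reply is that nothing need be lost. SAP 6.4.2.4 has the investigator judge every listed condition, and the CRF question refers to the protocol's definition, which is that list. The list itself calls ECOG above 1 a clinical progression, so the word is not confined to imaging. If the page can be completed without radiological PD, a yes could record any item. The CRF is not among the documents, so this cannot be excluded. A reader might infer from the wording that all non-imaging events are missed; the documents do not show that. What stands is that the SAP neither says the page is to be completed without a progression nor gives the date to use.

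A second reply is that Protocol 10.2.2.2 speaks of radiological progression, in which case one question attached to a progression fits. That reading conflicts with Protocol 10.2.3.2, the synopsis and SAP 6.4.2.4, and a progression death cannot merely qualify a scan. It is a further inconsistency to resolve.

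A third reply is that rule 3 covers only patients established as free of untreatable PD, so a progression death falls outside it, as the sensitivity analysis suggests. That is probably the intent. It is not written in rule 3, and such a death still has no stated indicator.

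**Conclusion.** The endpoint is under-specified as written. Its definition has seven items, and its only stated indicator is a question about a progression, with no event date for the non-imaging items. Those events can be missed and, if missed, are censored. The progression-death conflict between SAP 6.4.2.4, rule 3 and the sensitivity analysis stands whatever the CRF looks like.

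Two stronger conclusions may tempt a reader and are not supported. One is a count of affected patients: the documents give no share of non-imaging events, so any number would be an assumption. The other is that the derivation favours TheraSphere: the arms differ in when sorafenib starts, but the illustration shows bias in either direction. Its inputs are assumed and do not estimate this trial.

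The consequence is confined to TTUP and its place in the secondary hierarchy. The primary OS analysis is unaffected. The correction should be made, but it does not threaten the main result.

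**What to change.** First state whether TTUP is the first of any listed event or a radiological progression judged untreatable, and align Protocol 10.2.2.2 and 10.2.3.2 with SAP 6.4.2.4 and 8.6.2.2.

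If it is the first of any listed event:

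- Derive TTUP as the earliest of the CRF yes date, the first Child-Pugh above B7, confirmed ECOG above 1 (by the SAP 6.4.2.5 algorithm), and death due to progression.
- Add intolerance, contraindication and extra-hepatic disease where the eCRF records them with a date. Intolerance and contraindication need operational definitions. Extra-hepatic disease must be new since baseline, because eligibility criterion 19 admits some lung nodules and lymph nodes.
- Keep the Protocol 10.2.2.2 provision on Treatment-group lesions still amenable to TheraSphere, and say how it interacts with the derived dates.
- State in rule 3 that only deaths not due to progression are censored, and name the source for cause of death.
- Check for non-imaging events before applying rules 2 and 4.
- Report the CRF-question-only version as a sensitivity analysis, and tabulate first events by component and arm.

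The cost is SAP wording and some programming. ECOG and Child-Pugh dates are already collected. The downside is that derived dates partly replace investigator judgement, which the sensitivity analysis makes visible.

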6.4.2.5 Time to Symptomatic Progression

Time to symptomatic progression (TTSP) is defined as the time from date of randomization to date of assessment of ECOG performance status >1 with or without tumor progression based on investigator assessment according to RECIST criteria v1.1. The symptomatic progression is confirmed at the first two subsequent evaluations at least 8 and 16 weeks later, respectively. The date of the first ECOG performance status >1 will be used as the event date in the TTSP analysis (assuming ECOG performance status >1 at the first two subsequent evaluations at least 8 and 16 weeks later, respectively). Illustrative examples are provided in Table 7.

Table 7 Examples of Symptomatic Progression

Week X	Week X+8	Week X+16	Week X+24	Week X+32	TTSP Event
ECOG>1	ECOG>1	ECOG>1	ECOG≤1	ECOG≤1	Yes, event at Week X

ECOG>1	ECOG>1	Missing	ECOG>1	ECOG≤1	Yes, event at Week X
ECOG>1	Missing	ECOG>1	ECOG>1	Missing	Yes, event at Week X
ECOG>1	ECOG≤1	ECOG>1	ECOG>1	Missing	No
ECOG>1	No further ECOG assessments				No
ECOG>1	ECOG>1	No further ECOG assessments			No

Week X denotes that week of the first occurrence of ECOG >1

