8.6.2 Analysis of Secondary Efficacy Variables

For secondary efficacy endpoints, each comparison between treatment groups will be conducted at $\alpha=0.05$ (two-sided). Secondary study endpoints will be analyzed only at the final analysis to determine the statistical significance, if any, between the treatment groups. Study-wise Type I error will be controlled using a sequential hierarchical approach, as shown in the figure below. That is, if the primary comparison is statistically significant, the secondary endpoints will be analyzed as secondary endpoints in order of the list below and will continue as long as the obtained 2-sided probability is equal to or less than 0.05. If a probability of greater than 0.05 is obtained, the inferential analysis of secondary endpoints will stop and not proceed further down the ordered list. In this manner the overall study alpha is protected and no further adjustment for multiplicity of analyses is required. If a probability of greater than 0.05 is obtained for an endpoint then the analysis of that endpoint and the endpoints further down the ordered list will still be presented but will be considered as exploratory endpoints rather than secondary endpoints.

Hierarchical approach to control study-wise Type I error of primary and secondary efficacy endpoints

^a Type I error is controlled at $\alpha=0.05$ (two-sided) over the 2 planned interim analyses and final analysis.

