8.6.2.3 Time to Symptomatic Progression (TTSP)

TTSP rates will be derived from the Kaplan-Meier estimates for each treatment group; 3, 6, 9, and 12 month TTSP rates will be presented, together with 95% CIs. Quartiles will be presented and 95% CIs will be calculated on the quartiles for each treatment group. A log-rank (two-sided) test will be used to compare TTSP between the two treatment groups at a 0.05 significance level. The HR and corresponding 95% CI will be computed from a Cox proportional hazards model. Plots of the Kaplan-Meier curves will be provided for each treatment group. This analysis will be performed on both the mITT and PP populations.

TTSP (Months) = (Date of first ECOG >1/censor – Date of Randomization + 1)/ 30.4375.

The censoring is performed as follows:

- 1) If a patient does not have a post baseline ECOG assessment, then the TTSP will be censored at the randomization date, regardless of whether or not symptomatic progression has been observed.
- 2) If a patient received a subsequent HCC therapy before symptomatic progression or in the absence of symptomatic progression (note that for this scenario a subsequent HCC therapy may occur before the assessment of ECOG>1 or before either confirmation of ECOG>1 at the first two subsequent assessments at least 8 and 16 weeks later, respectively), the TTSP time will be censored at the last valid post baseline ECOG assessment on or before the start date of the subsequent HCC therapy. If the patient has no post-baseline ECOG assessments on or before the start date of the subsequent HCC therapy, the patient will be censored at the randomization date.
- 3) If a patient did not have a symptomatic progression and did not receive subsequent HCC therapy, the TTSP time will be censored at the last post baseline ECOG assessment date or at the randomization date if the patient does not have any post-baseline ECOG assessments.
- 4) If a patient had symptomatic progression immediately after two or more missed visits (note that for this scenario two or more missed visits may occur before the assessment of ECOG>1 or before either confirmation of ECOG>1 at the first two subsequent assessments at least 8 and 16 weeks later), the patient will be censored at the last post baseline ECOG assessment before the missed visits. If the patient has no post-baseline ECOG assessments before the missed visits, the patient will be censored at the randomization date.

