11.2 APPENDIX 2: STATISTICAL ANALYSIS AND PROGRAMMING DETAILS

The SAS procedure LIFETEST will be used in the Kaplan-Meier analyses. Patients who did not have an event will be censored.

The following code will be used:

```
proc lifetest data=all method=km alpha=0.05 outsurv=interval;  
    time aval*censr(1);  
    strata trtp;  
    id usbjid;  
run;
```

The SAS procedure PHREG will be used in the Cox regression analysis of time-to-event endpoints. Patients who did not have an event will be censored. The SAS method of discrete will be used to handle ties.

The SAS procedure MIXED will be used for mixed modeling. The following code will be used:

```
proc mixed method = reml;  
class BASE TRT VISIT SUBJID;  
model CH= BASE TRT VISIT TRT*VISIT /s ddfm=kr;  
repeated VISIT/type=UN subject=SUBJID;  
lsmeans TRT*VISIT /slice=VISIT diff alpha=0.05 cl;  
run;
```

where BASE is the baseline score, TRT is the assigned treatment, VISIT is the visit based on the window mapping, CH is the change from baseline.

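### TTSP treats a patient who deteriorates to ECOG >1 and dies before the second confirmation as event-free, and no planned TTSP analysis counts death; add two supplementary analyses

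*SAP*

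**What the plan says.** SAP 6.4.2.5 counts a TTSP event only when ECOG >1 persists: "The symptomatic progression is confirmed at the first two subsequent evaluations at least 8 and 16 weeks later, respectively". The event is dated back to the first ECOG >1. The last two rows of Table 7 show one or two ECOG >1 visits followed by "No further ECOG assessments", and both are classed as no event. Rows 2 and 3 let a later visit make up for a missed one.

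In SAP 8.6.2.3, rule 3 covers patients with no confirmed event and no subsequent HCC therapy: "the TTSP time will be censored at the last post baseline ECOG assessment date or at the randomization date". Rules 2 (subsequent therapy) and 4 (two or more missed visits) can censor earlier. None of the four rules mentions death, and the section has no sensitivity analysis.

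Other secondary endpoints do bring death in. Time to deterioration in QoL runs to the decline "or date of death, whichever occurs first" (SAP 6.4.2.3.2), and the TTUP definition includes "occurrence of new lesions after treatment, or death due to progression" (SAP 6.4.2.4).

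The two-visit confirmation comes from protocol 10.2.2.2, which is also silent on death. Formal testing of secondary endpoints depends on OS: "if the primary comparison is statistically significant, the secondary endpoints will be analyzed as secondary endpoints in order of the list below" (SAP 8.6.2).

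**The concern.** A missed visit can be made up later; death cannot. To be counted, a patient must survive at least 16 weeks after the first recorded ECOG >1. Patients who decline fastest are therefore the most likely to be recorded as never having declined, and the chance of being counted depends on survival after deterioration.

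TTSP is confirmatory only once OS has succeeded, which is when survival is most likely to differ between arms. If part of the survival gain falls after deterioration, more TheraSphere than control deteriorations get confirmed, and a real delay in deterioration can look weak or absent. From the planned TTSP output alone, a reader could not separate a weak effect on symptoms from events lost to early death.

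**Working it through.** **The plan's own figure.** The documents give no event count or power for TTSP, so the OS design is the anchor. The rho-family boundaries (rho = 1.5, one-sided 0.025) at 188, 250 and 417 deaths come out at z = 2.429, 2.431 and 2.093 (two-sided p = 0.0151, 0.0151, 0.0363, as stated). Power at a hazard ratio of 0.754 is 79.8%, against the stated 80%.

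**Deaths in the confirmation gap.** The gap is 16 weeks = 112/30.4375 = 3.68 months. With exponential survival and median m, P(death in the gap) = 1 − 2^(−3.68/m).
- At the design OS medians of 10.7 and 14.2 months (SAP 4.4): 21.2% and 16.4%. This is probably a floor, since these patients already have ECOG >1.
- At assumed medians after deterioration of 3, 4 and 6 months: 57%, 47% and 35%. In a control arm of 234 (half of the effective 468 in SAP Appendix 5) the simulation below gives 80 of 140, 74 of 157 and 63 of 182.

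**Hand approximation to the hazard ratio.** A deterioration counts only if the patient survives to the next visit (on average half of 8 weeks, so 4) and then 16 weeks more: 20 weeks = 140/30.4375 = 4.60 months. So

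TTSP HR ≈ k × S^r / S,

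where k is the true deterioration hazard ratio, r the hazard ratio for death after deterioration, and S = 2^(−4.60/m) in control. If r = 1, the last two terms cancel and there is no bias. With the full effect after deterioration (r = k):
- m = 3, k = 0.797: 0.797 × 0.429/0.346 = 0.99
- m = 4, k = 0.806: 0.806 × 0.526/0.451 = 0.94
- m = 6, k = 0.804: 0.804 × 0.652/0.588 = 0.89

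**Simulation.** 4,000 trials per scenario, 234 per arm, exponential times, visits every 8 weeks and all attended, censoring uniform over 18 to 78 months. Median time to death without deterioration is 30 months (assumed). Control is solved to a median OS of 10.7 months, and k is solved so that the OS hazard ratio is 0.754 (OS power 79% to 81%). Ties follow SAP Appendix 2: "The SAS method of discrete will be used to handle ties". Columns give m = 3/4/6 months.

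| Effect after deterioration | True HR (k) | TTSP HR as written | Power as written | Power if death confirms |
|---|---|---|---|---|
| None (r = 1) | 0.74/0.73/0.64 | 0.74/0.72/0.64 | 33/50/88% | 70/82/99% |
| Half (r = k^0.5) | 0.77/0.77/0.74 | 0.89/0.85/0.80 | 9/16/33% | 51/59/78% |
| Full (r = k) | 0.80/0.81/0.80 | 1.00/0.95/0.90 | 3/4/12% | 36/39/49% |

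The hand values for the full effect (0.99/0.94/0.89) agree with the simulated 1.00/0.95/0.90. Calibrating to OS medians of 10.7 and 14.2 instead gives 0.99/0.93/0.87 against a true 0.754 for the full effect. Those runs have OS power of 94% to 97%, above plan, so the table is the fairer guide.

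**Second model, with the supplementary analyses.** Assumptions: median 8 months to ECOG >1 and 30 months to death without it in control, 36-month cut-off. HRs are as written / (a) death before confirmation also counts / (b) the event in (a) or any death:
- HR 0.754 on onset and on death, m = 3: 1.00 / 0.79 / 0.75
- Same, m = 6: 0.87 / 0.78 / 0.76
- No effect on onset, death HR 0.6 after deterioration, m = 3: 1.44 / 1.07 / 0.99
- Onset HR 0.754, equal survival after deterioration, m = 3: 0.78 / 0.78 / 0.83. Events per 468 patients rise from 119 as written to 277 under (a).

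Neither model includes rules 2 and 4, telephone-only follow-up, recovery of ECOG, visit-window variation or the extra ECOG assessments at TheraSphere visits.

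**The case against.** The protocol defines TTSP as deterioration confirmed twice. Against that definition, death before confirmation is a competing event, and bias arises only when the hazard ratio is read as an effect on deterioration itself. This stands, and is why the main definition should stay. TTSP is also not alone in leaving death out: SAP 5.2.2 does so for TTP explicitly.

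The inputs that set the size (survival after ECOG >1, death without deterioration, the split of the effect) are not in the documents. That also stands; only the mechanism is free of them.

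A further objection is that OS, TTDQoL and the patient listings already let a reader count deaths after unconfirmed ECOG >1. The listings permit the count, but no planned table or TTSP estimate uses it. The ECOG shift table (SAP 8.8) is descriptive, and the TTP and TTUP sensitivity analyses only move a censoring date.

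A reader might infer that the rule could produce a false TTSP claim for TheraSphere. The calculations do not support that: wherever TheraSphere prolongs survival, the rule is neutral or works against it. A reader might also infer that the rule stops the testing hierarchy, since after a p-value above 0.05 "the inferential analysis of secondary endpoints will stop and not proceed further down the ordered list". TTSP's rank is in a figure not shown, so what would be stopped cannot be established, and supplementary analyses would not change it.

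**Conclusion.** The point holds as a gap in the TTSP analysis. Death before the second qualifying evaluation yields an event-free record, under rule 3 at a visit already at ECOG >1, and no planned analysis shows what this does to the result.

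The bias is conditional: immaterial if survival after deterioration is equal between arms, and otherwise against the longer-surviving arm. With assumed control medians of 3 to 6 months after deterioration and an OS hazard ratio of 0.754, the TTSP hazard ratio ranges from unbiased to about 1.00 to 0.90 against a true 0.80. Even without bias, events and power are lost, and the main analysis does not regain them under the fix.

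OS and its design figures are unaffected. The change is worth making because TTSP becomes confirmatory only after OS succeeds, and its hazard ratio would then be hard to interpret alone. Confidence is good on the mechanism and moderate on the size.

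**What to change.** Keep the two-visit confirmation as the main TTSP analysis and leave the hierarchy unchanged. Add to SAP 8.6.2.3, labelled supplementary and fixed before database hard lock:

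- **(a)** Also count an event, dated at the first ECOG >1, when the patient dies before the second qualifying evaluation under 6.4.2.5 took place or could have taken place, with no ECOG ≤1 in between. Define that time as the first scheduled visit at least 16 weeks later plus its window. A fixed 126 days (16 weeks plus 14) would miss about 7% to 11% of unconfirmed deaths when visits vary by ±14 days. Apply rules 2 and 4 as in the main analysis, and leave living patients without further assessment censored.
- **(b)** Time to the event in (a) or death from any cause, with the same censoring rules. Use only ECOG from the 8-weekly visits common to both arms, because the schedule of events adds ECOG assessments at TheraSphere work-up and administration with no control-arm match.
- Report by arm how many patients with unconfirmed ECOG >1 died, and interpret the main hazard ratio alongside (a) and (b).

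The cost is a little more analysis of ECOG and death data already collected. Some bias remains in (a): with no effect on deterioration and median survival after it of 6 months (TheraSphere) against 3 (control), it gives 1.11 where the rule as written gives 1.75. Analysis (b) mixes death with symptoms. SAP version 6.0 postdates the 30 April 2022 limit for the final analysis in an open-label trial, so the additions must not replace the main analysis.
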